Click Next to continue

20. I feel tense or wound up

Response is \*\*one\*\* of:

- Not at all
- Time to time, occasionally
- A lot of the time
- Most of the time

21. I still enjoy the things I used to enjoy

Response is \*\*one\*\* of:

- Definitely as much
- Not quite so much
- Only a little
- Hardly at all

22. I get a frightened feeling like something awful is about to happen

Response is \*\*one\*\* of:

- Not at all
- A little, but it doesn't worry me
- Yes, but not too badly
- Very definitely and quite badly

23. I can laugh and see the funny side of things

Response is \*\*one\*\* of:

- As much as I always could
- Not quite so much now
- Definitely not so much now
- Not at all

24. Worrying thoughts go through my mind

Response is \*\*one\*\* of:

- Only occasionally
- From time to time but not too often

- A lot of the time
- A great deal of the time

25. I feel cheerful

Response is \*\*one\*\* of:

- Most of the time
- Sometimes
- Not often
- Not at all

26. I can sit at ease and feel relaxed

Response is \*\*one\*\* of:

- Definitely
- Usually
- Not often
- Not at all

27. I feel as if I am slowed down

Response is \*\*one\*\* of:

- Not at all
- Sometimes
- Very often
- Nearly all of the time

28. I get a sort of frightened feeling like butterflies in the stomach

Response is \*\*one\*\* of:

- Not at all
- Occasionally
- Quite often
- Very often

29. I have lost interest in my appearance

Response is \*\*one\*\* of:

- I take just as much care as ever
- I may not take quite as much care
- I don't take as much care as I should
- Definitely

30. I feel restless as if I have to be on the move

Response is \*\*one\*\* of:

- Not at all
- Not very much
- Quite a lot
- Very much indeed

31. I look forward with enjoyment to things

Response is \*\*one\*\* of:

- As much as I ever did
- A bit less than I used to
- Definitely less than I used to
- Hardly at all

32. I get sudden feelings of panic

Response is \*\*one\*\* of:

- Not at all
- Not very often
- Quite often
- Very often indeed

33. I can enjoy a good book or radio or TV program

Response is \*\*one\*\* of:

- Often
- Sometimes
- Not often
- Very seldom

34. Over the last week or so, how often have you been bothered by the following problems?

(This is an information screen that requires no response)

Click Next to continue.

35. Feeling nervous, anxious or on edge

Response is \*\*one\*\* of:

- Not at all
- A couple of days
- More than half the days
- Nearly every day

36. Not being able to stop or control worrying

Response is \*\*one\*\* of:

- Not at all
- A couple of days
- More than half the days
- Nearly every day

37. Worrying too much about different things

Response is \*\*one\*\* of:

- Not at all
- A couple of days
- More than half the days
- Nearly every day

38. Trouble relaxing

Response is \*\*one\*\* of:

- Not at all
- A couple of days
- More than half the days
- Nearly every day

39. Being so restless that it is hard to sit still

Response is \*\*one\*\* of:

- Not at all
- A couple of days
- More than half the days
- Nearly every day

40. Becoming easily annoyed or irritable

Response is \*\*one\*\* of:

- Not at all
- A couple of days
- More than half the days
- Nearly every day

41. Feeling afraid as if something awful might happen

Response is \*\*one\*\* of:

- Not at all
- A couple of days

- More than half the days
- Nearly every day

42. The last few questions asked how often you were bothered by the problems. Now, please share how much distress the problem caused you:

Response is \*\*one position\*\* in this scale:

- 0 (No distress)
- 10
- 20
- 30
- 40
- 50
- 60
- 70
- 80
- 90
- 100 (Serious distress)

43. In the last week or so, how often have you experienced the following?

(This is an information screen that requires no response)

Click Next to continue.

44. I had sleep problems.

Response is \*\*one position\*\* in this scale:

- 1 (Never)
- 2
- 3
- 4
- 5
- 6
- 7 (Always)

45. I had nightmares.

Response is \*\*one position\*\* in this scale:

- 1 (Never)
- 2
- 3
- 4
- 5
- 6
- 7 (Always)

46. I had depression or felt dejected/downtrodden.

Response is \*\*one position\*\* in this scale:

- 1 (Never)
- 2
- 3
- 4
- 5
- 6
- 7 (Always)

47. I had jumpiness- I am easily frightened by sudden sounds or movements.

Response is \*\*one position\*\* in this scale:

- 1 (Never)
- 2
- 3
- 4
- 5
- 6
- 7 (Always)

48. I had the need to withdraw from others.

Response is \*\*one position\*\* in this scale:

- 1 (Never)
- 2
- 3
- 4
- 5
- 6
- 7 (Always)

49. I had irritability - I was easily agitated, annoyed or angered.

Response is \*\*one position\*\* in this scale:

- 1 (Never)
- 2
- 3
- 4
- 5
- 6
- 7 (Always)

50. I had frequent mood swings.

Response is \*\*one position\*\* in this scale:

- 1 (Never)
- 2
- 3
- 4
- 5
- 6
- 7 (Always)

51. I had a bad conscience, blamed myself, or had have guilty feelings.

Response is \*\*one position\*\* in this scale:

- 1 (Never)
- 2
- 3
- 4
- 5
- 6
- 7 (Always)

52. I had a fear of places or situations that remind me of the Intensive Care Unit.

Response is \*\*one position\*\* in this scale:

- 1 (Never)
- 2
- 3
- 4
- 5
- 6
- 7 (Always)

53. In the past week or so, I had muscular tension.

Response is \*\*one position\*\* in this scale:

- 1 (Never)
- 2
- 3
- 4 [default]
- 5
- 6
- 7 (Always)

54. The last few questions asked how often you were bothered by the problems. Now, please share show how much distress the problem caused you:

Response is \*\*one position\*\* in this scale:

- 0 (No distress)
- 10
- 20
- 30
- 40
- 50
- 60
- 70
- 80
- 90
- 100 (Serious distress)

55. Over the last 2 weeks, how much have you been bothered by any of the following problems?

(This is an information screen that requires no response)

Click Next to continue.

56. Pain

Response is \*\*one\*\* of:

- Not bothered at all
- Bothered a little
- Bothered a lot

57. Difficulty concentrating

Response is \*\*one\*\* of:

- Not bothered at all
- Bothered a little
- Bothered a lot

58. Weakness

Response is \*\*one\*\* of:

- Not bothered at all
- Bothered a little
- Bothered a lot

59. Feeling your heart pound or race

Response is \*\*one\*\* of:

- Not bothered at all
- Bothered a little
- Bothered a lot

60. Shortness of breath (or other breathing problems)

Response is \*\*one\*\* of:

- Not bothered at all
- Bothered a little
- Bothered a lot

61. Stiffness in joints or muscles

Response is \*\*one\*\* of:

- Not bothered at all
- Bothered a little
- Bothered a lot

62. Constipation or diarrhea

Response is \*\*one\*\* of:

- Not bothered at all
- Bothered a little
- Bothered a lot

63. Nausea, gas, or indigestion

Response is \*\*one\*\* of:

- Not bothered at all
- Bothered a little
- Bothered a lot

64. The last few questions asked how often you were bothered by the problems. Now, please share how much distress the problem caused you:

Response is \*\*one position\*\* in this scale:

- 0 (No distress)
- 10
- 20
- 30
- 40
- 50
- 60
- 70
- 80
- 90
- 100 (Serious distress)

65. In general, how would you rate your current quality of life?

Response is **\*\*one position\*\*** in this scale:

- 0 (Worst imaginable quality of life)
- 10
- 20
- 30
- 40
- 50 [default]
- 60
- 70
- 80
- 90
- 100 (Best imaginable quality of life)

66. Currently I am able to:

(This is an information screen that requires no response)

Click Next to continue.

67. ... bathe myself (either a sponge bath, tub bath, or shower)

Response is **\*\*one\*\*** of:

- Need no help
- Need some help or unable to do

68. ... dress myself (like putting on a shirt, buttoning and zipping, etc.)

Response is **\*\*one\*\*** of:

- Need no help
- Need some help or unable to do

69. ... feed myself (holding fork, cutting food, drinking from a glass)

Response is **\*\*one\*\*** of:

- Need no help
- Need some help or unable to do

70. ... get from a bed to a chair by myself

Response is **\*\*one\*\*** of:

- Need no help
- Need some help or unable to do

71. ... control my bladder or bowels

Response is \*\*one\*\* of:

- Need no help
- Need some help or unable to do

72. ... use the toilet by myself

Response is \*\*one\*\* of:

- Need no help
- Need some help or unable to do

73. ... use the telephone (including looking up numbers and dialing)

Response is \*\*one\*\* of:

- Need no help
- Need some help or unable to do

74. ... get to places beyond walking distance (drive own car or travel alone in buses or taxis)

Response is \*\*one\*\* of:

- Need no help
- Need some help or unable to do

75. ... go shopping for groceries or clothes

Response is \*\*one\*\* of:

- Need no help
- Need some help or unable to do

76. ... prepare my own meals

Response is \*\*one\*\* of:

- Need no help
- Need some help or unable to do

77. ... do housework em>(wash dishes, clean floors, etc.)

Response is \*\*one\*\* of:

- Need no help
- Need some help or unable to do

78. ... take my own medicine

Response is \*\*one\*\* of:

- Need no help
- Need some help or unable to do

79. ... handle my own money (write checks, pay bills)

Response is \*\*one\*\* of:

- Need no help
- Need some help or unable to do

80. How much do you agree or disagree with each statement?

(This is an information screen that requires no response)

Click Next to continue.

81. I never give up.

Response is \*\*one\*\* of:

- Totally disagree
- Disagree somewhat
- Neutral
- Agree somewhat
- Totally agree

82. I do everything to get well.

Response is \*\*one\*\* of:

- Totally disagree
- Disagree somewhat
- Neutral
- Agree somewhat
- Totally agree

83. I keep fighting to get better.

Response is \*\*one\*\* of:

- Totally disagree
- Disagree somewhat
- Neutral
- Agree somewhat
- Totally agree

84. I am afraid of pain.

Response is \*\*one\*\* of:

- Totally disagree
- Disagree somewhat
- Neutral
- Agree somewhat
- Totally agree

85. I can hardly tolerate pain.

Response is \*\*one\*\* of:

- Totally disagree
- Disagree somewhat
- Neutral
- Agree somewhat
- Totally agree

86. I am tough to myself when in pain.

Response is \*\*one\*\* of:

- Totally disagree
- Disagree somewhat
- Neutral
- Agree somewhat
- Totally agree

87. I view my illness as a personal learning experience.

Response is \*\*one\*\* of:

- Totally disagree
- Disagree somewhat
- Neutral
- Agree somewhat
- Totally agree

88. I am able to turn my illness into something positive.

Response is \*\*one\*\* of:

- Totally disagree
- Disagree somewhat
- Neutral
- Agree somewhat
- Totally agree

89. I use my illness in a creative way.

Response is \*\*one\*\* of:

- Totally disagree
- Disagree somewhat
- Neutral
- Agree somewhat
- Totally agree

90. I am gloomy about recovery.

Response is \*\*one\*\* of:

- Totally disagree
- Disagree somewhat
- Neutral
- Agree somewhat
- Totally agree

91. I feel the future is bleak.

Response is \*\*one\*\* of:

- Totally disagree
- Disagree somewhat
- Neutral
- Agree somewhat
- Totally agree

92. I do not believe in a happy ending.

Response is \*\*one\*\* of:

- Totally disagree
- Disagree somewhat
- Neutral
- Agree somewhat
- Totally agree

93. I resign myself to my destiny.

Response is \*\*one\*\* of:

- Totally disagree
- Disagree somewhat
- Neutral
- Agree somewhat
- Totally agree

94. I reconcile myself to the inevitable.

Response is \*\*one\*\* of:

- Totally disagree
- Disagree somewhat
- Neutral
- Agree somewhat
- Totally agree

95. I accept whatever will happen.

Response is \*\*one\*\* of:

- Totally disagree
- Disagree somewhat
- Neutral
- Agree somewhat
- Totally agree

96. Please indicate how frequently or infrequently you've been having each experience over the past 3 days, including today.

(This is an information screen that requires no response)

Click Next to continue.

97. I'm finding it difficult to stay focused on what's happening in the present.

Response is \*\*one\*\* of:

- Almost always
- Very frequently
- Somewhat frequently
- Somewhat infrequently
- Very infrequently
- Almost never

98. I'm rushing through activities without being really attentive to them.

Response is \*\*one\*\* of:

- Almost always
- Very frequently
- Somewhat frequently
- Somewhat infrequently
- Very infrequently
- Almost never

99. I'm doing jobs or tasks automatically, without being aware of what I'm doing.

Response is \*\*one\*\* of:

- Almost always
- Very frequently
- Somewhat frequently
- Somewhat infrequently
- Very infrequently
- Almost never

100. I'm finding myself preoccupied with the future or the past.

Response is \*\*one\*\* of:

- Almost always
- Very frequently
- Somewhat frequently
- Somewhat infrequently
- Very infrequently
- Almost never

101. I'm finding myself doing things without paying attention.

Response is \*\*one\*\* of:

- Almost always
- Very frequently
- Somewhat frequently
- Somewhat infrequently
- Very infrequently
- Almost never

102. Click Next to submit your answers and see your results.

(This is a score screen that requires no response)

103. Thank You!

(This is an information screen that requires no response)

Please click Next to exit the survey.

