#### **4. Study Objectives, Hypotheses, and Outcomes**

The overall objective of the pilot RCT is to determine the feasibility, acceptability and clinical impact of the intervention on patients' 1- and 3-month psychological distress symptoms of a self-directed mobile coping skills training (mCST) intervention, known as "Blueprint" as compared to usual care control.

The primary hypothesis in which this study is based is that the mCST will be feasible and acceptable based on comparison of observed to priori benchmarks.

The second hypothesis is compared to usual care, the mCST use by enrolled subjects will lead to improvement in symptoms of psychological distress via the HADS and PTSS at the 1- and 3-month mark post randomization.

The primary outcome of the pilot RCT is centered on acceptability and feasibility. The Client Satisfaction Questionnaire 8 will measure acceptability with open-ended participant feedback completed at the time of T3, which is considered end of study (EOS). Feasibility will be measured by frequency of randomization, retention, and adherence. Secondary outcomes are HADS and PTSS scores at 1 and 3 months post-randomization.

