## 9. Statistical Design, Analyses Plan, and Sample Size and Power

### Statistical Design and Analyses Plan

The primary goal of this 3-arm pilot RCT is to explore the feasibility and acceptability of mCST to inform a definitive future clinical trial. To do so, we will test differences between observed and a priori-defined benchmarks among mCST recipients using t-tests for continuous variables and chi-square tests for categorical variables.

The secondary goal is to estimate a reasonable range of clinical effect of mCST in comparison to a usual care control condition. General linear models will be used to estimate mean changes and corresponding 95% confidence intervals (CIs) in psychological distress (i.e., HADS and PTSS scores) for each treatment group over the 3 months of post-randomization follow-up using SAS PROC MIXED (SAS Institute, Cary NC). We will fit the models with an unstructured covariance matrix to better understand and represent the correlation between patients' repeated measures. We will also use similar modeling strategies to explore how the key clinical characteristics (e.g., history of ICU delirium, illness severity, diagnosis grouping), objective physical characteristics (e.g., functional status), sociodemographic factors, and mechanistic elements (e.g. self-efficacy) described in the conceptual model are associated with changes in psychological distress both within and between treatment groups. While for main analyses we will pool all mCST participants in comparisons with usual care control, we will also perform exploratory analyses similar to those described above to compare all three groups as well.

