- Very frequently
- Somewhat frequently
- Somewhat infrequently
- Very infrequently
- Almost never

101. I'm finding myself doing things without paying attention.

Response is \*\*one\*\* of:

- Almost always
- Very frequently
- Somewhat frequently
- Somewhat infrequently
- Very infrequently
- Almost never

102. Please help us improve the Blueprint program by answering some questions about it. We are interested in your honest opinion, whether positive or negative.

(This is an information screen that requires no response)

Click Next to continue.

103. How would you rate the quality of the Blueprint program?

Response is \*\*one\*\* of:

- Excellent
- Good
- Fair
- Poor

104. Did you get the kind of program that you wanted?

Response is \*\*one\*\* of:

- Yes, definitely
- Yes, generally
- No, not really
- No, definitely not

105. To what extent has the Blueprint program met your needs?

Response is \*\*one\*\* of:

- Almost all of my needs have been met
- Most of my needs have been met
- Only a few of my needs have been met
- None of my needs have been met

106. If a friend were in need of similar help, would you recommend the Blueprint program to him or her?

Response is \*\*one\*\* of:

- Yes, generally

- Yes, generally
- No, not really
- No, definitely not

107. How satisfied are you with the amount of help you received in the Blueprint program?

Response is **\*\*one\*\*** of:

- Very satisfied
- Mostly satisfied
- Indifferent or mildly dissatisfied
- Quite dissatisfied

108. Has the Blueprint program helped you to deal more effectively with your problems or stresses?

Response is **\*\*one\*\*** of:

- Yes, it helped a great deal
- Yes, it helped somewhat
- No, it really didn't help
- No, it seemed to make things worse

109. In an overall, general sense, how satisfied are you with the Blueprint program?

Response is **\*\*one\*\*** of:

- Very satisfied
- Mostly satisfied
- Indifferent or mildly dissatisfied
- Quite dissatisfied

110. If you were to decide about participating or not in the Blueprint program, would you do it again?

Response is **\*\*one\*\*** of:

- Yes, definitely
- Yes, I think so
- No, I don't think so
- No, definitely not

111. Could you provide any comments about specific ways the Blueprint program helped or didn't help you?

Response is **\*\*free-form text\*\***.

112. Click Next to submit your answers and see your results.

(This is a score screen that requires no response)

113. Thank You!

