3.3 Other Variables of interest

Variable	Dataset	Description	Specifications

4 Statistical Analysis Plan

All analyses will be done using SAS 9.4. Continuous variables will be summarized with mean/standard deviation/median/Q1-Q3/range and categorical variables with frequency counts and percentages. Number of missing data for each variable will be reported.

4.1 Analysis Plan for Primary Aim 1

1. First, we will describe our cohort. In Table 1 we will summarize participant characteristics overall and by arm. No statistical tests will be provided as this was a randomized trial, and ideally groups should be balanced.
2. To assess Aim 1 for feasibility and acceptability we will evaluate CSQ-8 and SUS scores. Results will be reported in Table 2.

4.2 Analysis Plan for Primary Aim 2

1. To address Aim 2, we will describe the secondary outcomes at each time point by arm, as well as the change in scores at T2 and T3 from T1 in Table 3. Any additional secondary outcomes will be described in this table.
2. To assess if there was change at each timepoint of interest between the arms we estimate mean changes (and 95% CI) from baseline to each timepoint for each distress outcome (HADS, PTSS) using a general linear model (PROC MIXED). Model parameters will include treatment arm (1, 2, 3), time indicator (T1, T2, T3), and an arm by time interaction term. Change estimates and CI's will be reported in Table 4. To quantify clinically important differences, rather than report p-values which is not recommended for pilot studies with

small sample sizes, we will compare the estimated group mean differences and 95% CI's to half (0.5) of the baseline standard deviation (SD) of each outcome score.

5 Appendix I: Planned figures and tables

Figure 1: CONSORT Diagram

Table 1: Demographic characteristics of participants at baseline

Characteristic	Arm 1: Intervention Group 1 (Blueprint + Therapist) N=	Arm 2: Intervention Group 2 (Blueprint only) N=	Arm 3: Control (Usual Care) N=	Total N=
Stratification Variables				
Age				
<50				
≥50				
ICU Service				
Medical				
Surgical				
Baseline HADS				
<14				
≥14				
Other Baseline Characteristics				
Age				
Mean (sd)				
Median				
Q1, Q3				
Range				
Gender				
Male				
Female				

Table 2: Feasibility and Acceptability

Characteristic	Arm 1: Intervention Group 1	Arm 2: Intervention Group 2	Arm 3: Control (Usual Care)	Total N=

	(Blueprint + Blueprint Therapist) N=		N=
	N=	N=	
Feasibility			
% Consented	--	--	--

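### As printed, the CSQ-8 'recommend' item in the T2 survey repeats one answer label and omits the strongest yes, so it cannot separate its top two response categories

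*Protocol*

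**What the plan says.** Protocol section 4 states that "The primary outcome of the pilot RCT is centered on acceptability and feasibility", and that "The Client Satisfaction Questionnaire 8 will measure acceptability with open-ended participant feedback completed at the time of T3". Protocol section 3 likewise lists the CSQ-8 at T3 only.

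In Appendix 3, the eight satisfaction items appear in the T2 survey as items 103–110. Item 106 asks "If a friend were in need of similar help, would you recommend the Blueprint program to him or her". Its first and second answers are both "Yes, generally"; the other two are the mild and the definite no. Item 104, "Did you get the kind of program that you wanted", prints the same family of answers with four different labels, starting with the definite yes. The printed T3 survey (Appendix 3 I) has no satisfaction items.

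On analysis, the protocol's Statistical Design and Analyses Plan says "we will test differences between observed and a priori-defined benchmarks among mCST recipients using t-tests for continuous variables". SAP section 4.1 says "To assess Aim 1 for feasibility and acceptability we will evaluate CSQ-8 and SUS scores". The only acceptability row in SAP Table 2 is the CSQ score. SAP section 3.1 lists the CSQ-8 without a time point, an item scoring rule or a benchmark.

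**The concern.** A respondent who reads two identical answers cannot know which one stands for the stronger endorsement. The item therefore loses the distinction between a definite and a general recommendation, among exactly the patients who are favourable to the programme. If the two lines carry different codes, patients with the same opinion can score one point apart. If they carry the same code, nobody can reach the top of the item.

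The CSQ total is the acceptability figure the SAP plans to tabulate. More patients would not remove a net bias from this source, and the lost distinction cannot be recovered from the stored answers. Protocol section 14 (Quality Assurance and Confidentiality) says the data system forces answers to key items such as primary outcome surveys, so a patient who finds no fitting label may be unable to skip the item. With no scoring or handling rule in the SAP, the treatment of this item would be chosen after the data are seen.

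**Working it through.** **No figure to reproduce.** Neither document states a CSQ-8 range, cut-off, standard deviation or benchmark. The check is a comparison of printed labels, followed by bounds under stated assumptions.

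**Labels side by side (Appendix 3 H).**

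| Position | Item 104 | Item 106 |
|---|---|---|
| 1 | definite yes | general yes |
| 2 | general yes | general yes |
| 3 | mild no | mild no |
| 4 | definite no | definite no |

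Item 106 has four options, like the other seven CSQ-8 items. One label has replaced another; no line has been added.

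**Range, assuming each item is scored 1–4 and summed.** Minimum 8 × 1 = 8; maximum 8 × 4 = 32; range 24. If both duplicated options score 3, the maximum is 7 × 4 + 3 = 31. One patient's error is at most 1 point, or 1/24 = 4.2% of the range.

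**Size among positive responders.** Let r be the share who mean a definite yes and q the chance of choosing the first of the two identical lines, taken as equal for everyone.

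- Coded by position: share given the wrong item score = r(1 − q) + (1 − r)q; mean bias = −r(1 − q) + (1 − r)q.
- Coded by label (both score 3): share wrong = r; mean bias = −r.

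Neither r nor q is in the documents. The table covers r from 0.3 to 0.9; each cell gives mean bias in points, then share wrong.

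| r | Position, q = 0 | Position, q = 0.5 | Position, q = 1 | Label |
|---|---|---|---|---|
| 0.3 | −0.3, 30% | +0.2, 50% | +0.7, 70% | −0.3, 30% |
| 0.5 | −0.5, 50% | 0.0, 50% | +0.5, 50% | −0.5, 50% |
| 0.7 | −0.7, 70% | −0.2, 50% | +0.3, 30% | −0.7, 70% |
| 0.9 | −0.9, 90% | −0.4, 50% | +0.1, 10% | −0.9, 90% |

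Worked cell, r = 0.7 and q = 0.5: bias = −0.7 × 0.5 + 0.3 × 0.5 = −0.2; share wrong = 0.35 + 0.15 = 0.50. Over all respondents, multiply the bias by the share who answer positively.

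**Scale against sampling error.** Assume a standard deviation of the CSQ total of 4 to 6, with every app patient answering. Protocol section 2 plans 25 + 25 = 50 app patients: standard error 4/√50 = 0.57 to 6/√50 = 0.85. SAP section 2 targets 15 + 15 = 30: 4/√30 = 0.73 to 6/√30 = 1.10. The largest bias in the table, 0.9 points, would be about 0.8 (0.9/1.10) to 1.6 (0.9/0.57) standard errors if all respondents were positive. Several cells give a small bias or none.

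**The case against.** **It may be only a printing fault.** A page break appears to fall between the two identical answers, and Appendix 3 has other rough spots: a second Week 1 check-in under a Week 2 heading, and helpfulness questions in Week 4 anchored in terms of confidence. A line repeated at a page break would leave five options with the definite yes still present, so a reading artefact is unlikely. A print error that is absent from the live app cannot be excluded. That part of the objection stands.

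**The link to the primary score is not secure.** The protocol places the CSQ-8 at T3, while the faulty item is in the T2 survey. The documents do not show which form supplies the acceptability score. This stands, and it is a conflict that needs settling in its own right. It does not clear the item, because no correct copy of the CSQ-8 is printed anywhere else.

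**The effect is small and the trial is a pilot.** One item of eight is affected, SAP section 4.1 also names SUS scores, open-ended feedback is collected, and no CSQ-8 benchmark is given. No decision can be shown to change. This stands and limits the size of the point.

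**Stronger readings.** A reader might infer that the acceptability score is wrong for most satisfied patients. The documents do not support that: the share affected ran from 10% to 90% under the assumptions tried, and the mean bias can be positive, negative or zero. A reader might also infer that the top score cannot be recorded. Under position coding a first option still exists and may store the top code; what is lost is its label.

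**Conclusion.** The point holds for the form as printed. Item 106 cannot separate its top two categories, and it belongs to the measure that carries acceptability in the primary outcome. Under assumed 1–4 scoring the error is at most 1 point per patient on a 24-point range, for an unknown share of positive responders and in a direction set by the coding; coded by label, the maximum total is 31 instead of 32. The size rests on the assumed scoring, response shares and standard deviation. Whether any patient saw the faulty item is not known from the documents. It deserves correction because the remedy is nearly free and the item sits inside a primary measure, not because a conclusion has been shown to be wrong.

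**What to change.** 1. Change the first answer of item 106 to the definite yes, matching item 104, in every survey that carries the CSQ-8.
2. Check the deployed app for the labels shown and for how each option is coded.
3. Reconcile the timing: Protocol sections 3 and 4 put the CSQ-8 at T3, whereas Appendix 3 prints it only in the T2 survey. State in the SAP which time point supplies the acceptability score.
4. If any responses were collected on the faulty form, add to SAP section 4.1 that the CSQ total is reported both as collected and without item 106, for example prorated from the other seven items (sum × 8/7). Collapsing the top two categories of item 106 is also defensible, since its yes/no information is intact. The choice should be fixed before the scores are examined.

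The cost is one label, one check of the app and a short addition to the SAP. The small downside is a less complete total for patients who answered the faulty form.
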